8.4 New Safety Information

8.4.1 Definition of New Safety Information (NSI)

The Office for Human Research Protections (OHRP) considers unanticipated problems involving risks to participants or others as NSI and this includes, in general, any incident, experience, or outcome that meets all of the following criteria:

- Unexpected in terms of nature, severity, or frequency given (a) the research procedures/study treatment that are described in the protocol-related documents, such as the Institutional Review Board (IRB)-approved research protocol, the informed consent document, and Investigator's Brochure (IB); and (b) the characteristics of the participant population being studied;
- Related or possibly related to participation in the research ("possibly related" means there is a reasonable possibility that the incident, experience, or outcome may have been caused by the procedures/treatment involved in the research); and
- Suggests that the research places participants or others at a greater risk of harm (including physical, psychological, economic, or social harm) than was previously known or recognized.

8.4.2 NSI Reporting

The investigator will report NSI to the UNC IRB. The NSI report will include the following information:

- Protocol identifying information: protocol title and number, PI's name, and the IRB project number;
- A detailed description of the event, incident, experience, or outcome;
- An explanation of the basis for determining that the event, incident, experience, or outcome represents an NSI;
- A description of any changes to the protocol or other corrective actions that have been taken or are proposed in response to the NSI.

To satisfy the requirement for prompt reporting, NSI reports will be reported using the following timeline:

- NSI that are serious adverse events (SAEs) will be reported to the IRB and the DAIDS MO within 3 business days of the investigator becoming aware of the event.
- Any other NSI will be reported to the IRB and to the DAIDS MO within 7 business days of the investigator becoming aware of the event.
- All NSI should be reported to appropriate institutional officials (as required by an institution's written reporting procedures), the NIH MO (or designee), and the Office for Human Research Protections (OHRP) within 30 business days of the IRB's review and determination that the report of the problem from the investigator imposed a safety risk.

8.4.3 Reporting NSI to Participants

We would inform all study participants by letter or electronic messaging of any NSI if it is determined by the UNC IRB to merit such notice.

9 STATISTICAL CONSIDERATIONS

This is a phase I, single-site, pilot study to evaluate the safety of **M3** and **M4** given individually or in combination to HIV-infected individuals suppressed on ART. There are two secondary analyses and multiple exploratory objectives to measure the effect of this therapy on HIV-specific T cell responses and on persistent HIV infection.

9.1 Statistical Hypotheses

Hypothesis

Intramuscular (IM) vaccination with **M3** or **M4**, given individually or in combination (**M3+M4**) in adult HIV-infected participants on suppressive combination antiretroviral therapy (ART) will be safe and increase HIV-1-specific T cell responses targeting conserved regions of HIV-1.

The simultaneous administration of **M3** with **M4** (**M3+M4**) will result in a greater increase in the breadth of HIV-1-specific T cells targeting conserved regions of HIV-1 than with the individual administration of **M3** or **M4** alone.

9.2 Sample Size Determination

9.2.1 Primary Sample Size Consideration

From previous publications employing MVA- vectored vaccines, the proposed number of participants (7 vaccinees per arm and 3 placebo controls) is sufficient to evaluate the risk

of SAEs or severe local or systemic reactions in the study population. Descriptive analyses will be used to summarize AEs or SAEs in each arm as well as combined MVA arms.

Enrollment into the trial will be suspended if two participants experience a study treatment-related toxicity of Grade 3 or higher or if one or more participants experience an SAE possibly related to study treatment (See Section 10.1.6). If zero of 7 participants experience a safety event, a 95% 1-sided exact binomial upper confidence limit for the probability of a safety event will be 35%. If one participant experiences a safety event, the corresponding 95% 1-sided upper confidence limit will be 52%. Each safety endpoint will be estimated with an exact binomial 95% 1-sided upper confidence limit. If zero safety events are observed in the three vaccine arms and data are pooled across arms (n=24), then the upper limit of the exact, 1-sided 95% confidence interval (CI) will be 13%.

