Occurrence of at least one \geq Grade 3 Adverse Event (AE) including signs/symptoms, lab toxicities, and/or clinical events, that is possibly, probably or definitely related to study treatment any time from the first day of treatment through 28 days following vaccination.

Secondary Endpoint: Safety

Occurrence of any \geq Grade 1 AE including signs/symptoms, lab toxicities, and/or clinical events, that is possibly, probably, or definitely related to study treatment any time from the first day of treatment through Day 168 (Week 24) following vaccination.

Safety data will include local and systemic signs and symptoms, laboratory measures of safety/toxicity, and all adverse and serious adverse events. Safety data will be routinely collected throughout the duration of the study.

NOTE: The occurrence of a Grade 3 elevated blood pressure during a study-related leukapheresis that resolves following completion of the procedure will not be included as a primary safety endpoint.

Secondary Endpoints: Immunogenicity

Relative change in magnitude of T cell responses to HIV-1 conserved regions from pre-vaccination (Day 0) to post-vaccination at Day 7 and Day 14.

Change in breadth of T cell responses targeting HIV conserved regions from pre-vaccination (Day 0) to post-vaccination at Day 28.

Study Population: HIV-infected men and women ≥ 18 and ≤ 65 years of age with viral suppression on ART as measured on standard HIV RNA assays. Eligible participants must have a CD4 cell count ≥ 350 cells/mm³ at screening.

Phase: Phase 1

Description of Facilities Enrolling Participants: Single site - The University of North Carolina, Chapel Hill, North Carolina, USA.

Description of Study Intervention: This is a double blind, randomized, placebo-controlled, parallel design, study in which 24 HIV-infected participants with durable viral suppression will be randomly assigned to receive vaccination with MVA.tHIVconsV3 (M3), MVA.tHIVconsV4 (M4), M3+M4 combined, or placebo.

Participants will be randomized 7:7:7:3 to one of four study arms, and receive study treatment or placebo at Day 0.

Study Schema

Arm	N	Day	Treatment	Dose (pfu)	Route
1	7	0	M3	2×10^8	IM
2	7	0	M4	2×10^8	IM
3	7	0	M3+M4	1×10^8 , each vaccine	IM

[figure not shown]
4	3	0	Placebo (saline)	-	IM
---	---	---	---------------------	---	----

M3 = MVA.tHIVconsv3
M4 = MVA.tHIVconsv4
pfu = plaque forming units
IM = intramuscular

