8.2.9 Post Vaccination Symptom Log

Participants will be given a “Post vaccination symptom log” to use as a memory aid for tracking adverse events that occur during the 3 days following the injection. Participants will record daily temperature and systemic symptoms.

1. For this study, solicited AEs occurring during the 3 days after the vaccine/placebo injection will include:
 - unusually tired/feeling unwell
 - muscles aches
 - headache
 - chills
 - nausea
 - joint pain
2. Instruct participants to take their temperature at least once daily, starting with the day of injection (Day 0), after leaving the clinic and through Day 3 post-injection.
3. Temperature should be taken orally in the evening whenever possible. If more than one measurement is made in a day (for example due to feeling unwell), then the highest temperature taken that day should be recorded.
4. The symptoms and assignment of grades will be reviewed with participants to assure an understanding of how to use and evaluate each symptom during these first 3 days.

The study coordinator will discuss the symptom logs for accuracy and completeness at Day 2 and review and collect the completed symptom log at the Day 7 Visit. The study coordinator will review symptoms with participants for each identified symptom and clarify the grading assigned at the time. Additionally, active solicitation of AEs will be done at every visit. Participants will also be asked to contact the study coordinator, study PI, or designee should they experience any adverse events at any time points during the study.

8.2.10 *Solicited AE Assessments:*

The study coordinator will assess for Solicited AEs (expected) symptoms at Day 2 and Day 7 following each injection.

Assessments will consist of a standard series of questions administered at approximately 48 hours post vaccination (Day 2) and at the Day 7 Visit. The following local reaction evaluations ([Table 9](#)) and systemic reaction evaluations ([Table 10](#)) are part of each assessment.

Table 9 Local Reaction Solicited AE Assessments

Injection site erythema (redness)	Injection site pruritus (itching)
Injection site tenderness	Injection site swelling

Warmth at injection site	Skin discoloration
Injection site pain	Skin damage (vesiculation or ulceration)
Induration (hardening or formation of a crust or scab)	

Table 10 Systemic Reaction Solicited AE Assessments

Vomiting	Fatigue (extreme tiredness)
Malaise	Headache

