8.3.4 Adverse Event Reporting

Adverse events will be graded according to the DAIDS Table for Grading the Severity of Adult and Pediatric Adverse Events (DAIDS AE Grading Table), corrected Version 2.1, July 2017, on the DAIDS RSC website at <http://rsc.tech-res.com/clinical-research-sites/safety-reporting/daids-grading-tables>.

The study will monitor participants for adverse events. Toxicities will be characterized in terms including duration, intensity, and time to onset. Safety endpoints will include all adverse experiences, in addition to laboratory safety assessments, and vital signs. All AEs will be recorded on the appropriate study form.

AEs will be recorded in the database if any of the following criteria have been met:

- Study-related Grade ≥ 1 AEs
- Grade ≥ 3 AEs
- Autoimmune-related AEs regardless of grade
- HIV viral loads ≥ 50 copies/mL
- Injection reactions regardless of grade
- AEs that led to a change in study intervention regardless of grade
- AEs meeting SAE definition or EAE (Expedited Adverse Event) reporting requirement

Grade 1 or 2 Toxicity

Participants who develop a Grade 1 or 2 AE or lab toxicity that occurs following a vaccine/placebo injection that is thought to be possibly, probably, or definitely related to the study treatment should be discussed with the study team. Grade 1 or 2 AEs that may be related to the vaccine/placebo injection will be handled according to standard clinical practice and documented.

Grade 3 Toxicity

For participants who develop a Grade 3 AE following the administration of vaccine/placebo judged by the study PI (or designee) to be at least possibly study treatment-related, the protocol team must be notified within 24 hours. Participants experiencing Grade 3 AEs should be followed closely and if the AE does not return to

Grade ≤ 2 within 2 weeks, the study team should again be notified within 24 hours and the SMC will be notified.

For participants who experience a Grade 3 AE judged not related to the study treatment by the investigator, continued study participation is at the discretion of the study PI (or designee) in consultation with the protocol team and SMC.

Grade 4 Toxicity

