9.3.8 Safety Analyses

For the safety endpoints, we will describe all study treatment-related AEs through Day 28 (primary endpoint) and the end of study (secondary endpoint). AEs will be coded per the Medical Dictionary for Regulatory Activities (MedDRA). Events prior to treatment (e.g., due to study-related procedure) will be listed separately in an appendix to the final clinical study report. The following tables of AE data will be created to summarize the number and percent of participants who experience at least one event of each of the following types:

- Study treatment-related AEs by severity grade
- All SAEs (this may be a listing if there are few events)
- Study treatment-related SAEs
- Fatal AEs (this may be a listing if there are few events)
- AEs that result in study discontinuation or study treatment discontinuation
- AEs categorized as AESI
- AEs with severity Grade 3 or greater
- Study treatment-related AEs with severity Grade 3 or greater
- All treatment-related AEs with severity Grade 1 or greater

All of these tables will display the number and percent of participants that experience the given event and will display events by System Organ Class (SOC) and Preferred Term (PT). Events will be displayed alphabetically for SOC and in descending order of overall PT incidence within each SOC.

9.3.9 *Tabulation of Individual Participant Data*

Individual participant data will be listed by measure and time point.

9.3.10 *Exploratory Analyses*

Other objectives or exploratory analysis can be grouped into additional immunological measures and virologic measures.

Immunologic measures: Kinetic data will be analyzed by descriptive statistics and graphical displays. Other observed immunologic measurements such as virus inhibition may not be normally distributed or may be partially censored due to assay limits of quantification, and thus, an exact Wilcoxon signed-rank test will be used for within-participant comparisons.

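### The one-sided upper limit planned for every safety endpoint suits rare Grade ≥3 events but says little about the Grade ≥1 endpoint, and no listed table shows solicited reactions regardless of attribution

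*Combined protocol and SAP*

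**What the plan says.** The Synopsis and Section 3 define two safety endpoints. The primary is at least one related Grade 3 or higher adverse event (AE) in the 28 days after vaccination. The secondary is any Grade 1 or higher AE "that is possibly, probably, or definitely related to study treatment any time from the first day of treatment through Day 168 (Week 24) following vaccination".

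On intervals, Section 9.2.1 says: "Each safety endpoint will be estimated with an exact binomial 95% 1-sided upper confidence limit". Section 9.3.3 repeats this for the primary endpoint and adds the proportion. Section 9.3.4 has no text of its own for the secondary safety endpoint. Section 9.3.5 keeps two-sided 95% intervals for efficacy and exploratory proportions. No lower bound is therefore planned for either safety endpoint.

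Other safety output is planned. Section 9.2.1 promises descriptive summaries for each arm and for the combined MVA arms. Section 9.3.8 lists tables of number and percent of participants by system organ class and preferred term, and Section 9.3.9 adds individual listings. The low-grade tables in Section 9.3.8 are "Study treatment-related AEs by severity grade" and a table of treatment-related events of Grade 1 or above.

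On collection, Section 8.2.10 says: "The study coordinator will assess for Solicited AEs (expected) symptoms at Day 2 and Day 7 following each injection". Tables 9 and 10 give the local and systemic symptoms, and a participant log covers the first three days. On data entry, Section 8.3.4 says: "AEs will be recorded in the database if any of the following criteria have been met". Under that list a Grade 1 or 2 event enters mainly if it is study-related or an injection reaction. The remaining criteria are narrow: autoimmune events, a viral load of 50 copies/mL or more, a change in study intervention, and serious or expedited events.

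**The concern.** An upper limit answers the question of how large a risk could be. That is the right question when few or no severe events are seen. For an event that most vaccinees may have, the upper limit sits near 100% whatever the data. The useful statement is then the smallest rate compatible with the data, and the plan has no interval that gives it.

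The second gap concerns attribution. Symptoms are asked of every participant, placebo recipients included, so they could be compared by arm without any causality judgement. The routine low-grade tables apply that judgement first. A mild solicited headache rated unrelated would appear in none of the tables unless it was serious, of special interest or led to discontinuation.

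This matters moderately. Section 10.1.6 describes the study as first-in-human, safety is its primary objective, and Section 4.2 says its results will guide which MVA strategy goes into the next study.

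**Working it through.** **Inputs.** There are 7 participants per vaccine arm, 21 vaccinees pooled and 3 on placebo (Table 6). The method is exact binomial, 95%, one-sided upper (Section 9.2.1). The documents give no expected rate of any related Grade 1 or higher AE. Section 2.3.1 anticipates transient Grade 1–2 local reactions, headache, malaise and fever. Section 2.2.4 reports malaise alone in 7 of 15 (47%) recipients of the earlier MVA vaccine.

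**Formulas (Clopper-Pearson).** For x events in n participants:
- One-sided 95% upper limit: the 0.95 quantile of Beta(x+1, n−x), or 100% if x = n.
- Two-sided 95% interval: the 0.025 quantile of Beta(x, n−x+1) to the 0.975 quantile of Beta(x+1, n−x).

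**The plan's own figures.** 0/7 gives 1 − 0.05^(1/7) = 34.8% (stated 35%). 1/7 gives 52.1% (stated 52%). Both reproduce. The pooled 13% for zero events reproduces with n = 21 (13.3%) but not with the printed n = 24 (11.7%). That is a separate slip and does not affect this point.

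**The same method at higher counts.** The counts are assumed, to show the range.

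| Events | One-sided 95% upper | Two-sided exact 95% CI |
|---|---|---|
| 3/7 | 77.5% | 9.9–81.6% |
| 4/7 | 87.1% | 18.4–90.1% |
| 5/7 | 94.7% | 29.0–96.3% |
| 6/7 | 99.3% | 42.1–99.6% |
| 7/7 | 100% | 59.0–100% |
| 18/21 | 96.0% | 63.7–97.0% |
| 19/21 | 98.3% | 69.6–98.8% |
| 20/21 | 99.8% | 76.2–99.9% |

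Two of these can be checked by hand. For 6/7 the upper limit solves 1 − p^7 = 0.05, so p = 0.95^(1/7) = 99.3%. For 7/7 the two-sided lower bound solves p^7 = 0.025, so p = 0.025^(1/7) = 59.0%.

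**How often the limit would reach 99%.** This needs at least 6/7 in an arm or 20/21 pooled. By assumed true rate:

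| True rate | P(at least 6/7) | P(at least 20/21) |
|---|---|---|
| 47% | 4% | under 0.1% |
| 75% | 44% | 2% |
| 80% | 58% | 6% |
| 90% | 85% | 36% |
| 95% | 96% | 72% |

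**Recording rules side by side.**
- Section 8.1: post-entry signs and symptoms of Grade 2 or above are recorded, and related ones at any grade.
- Section 8.3.3: all AEs, including local and systemic reactions, are documented whatever their relationship to treatment.
- Section 8.3.4: database entry depends on the criteria above. The same section says that injection-site erythema or induration without functional interference is not counted as an AE, yet its criteria record injection reactions at any grade.
- Section 10.1.9.1: expected adverse reactions data are entered in the database.

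These rules do not settle whether a Grade 1 systemic symptom judged unrelated reaches the database. Whichever rule governs, Section 9.3.8 lists no table that would show it.

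**The case against.** The strongest reply is that the interval is only one output. Numbers and percents by arm, grade, organ class and term are planned, with individual listings, and Section 9.3.2 puts the emphasis on descriptive summaries. This stands. A reader might infer that the study cannot describe reactogenicity, but the planned tables do describe reactions judged related.

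A reader might also infer that the upper limit will be 99–100% at the expected rates. The documents give no such rate. The 7 of 15 figure concerns one symptom in a study with a three-dose schedule, whereas this trial gives a single dose. It corresponds to about 3/7, with a limit of 77.5%. The rate of any AE in that study cannot have been lower, but how much higher is unknown.

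A third tempting inference is that attribution will remove a material share of symptomatic participants from the endpoint. The documents do not support any number. The endpoint is per participant, so every symptom in that person would have to be rated unrelated. Section 8.3.2.2 requires an alternative cause for that rating and lets the possible category stand even when another cause may exist. Assessment is also blinded.

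Finally, Sections 8.1, 8.3.3 and 10.1.9.1 may already capture most of the data, no decision rule uses this limit, and anyone can compute a two-sided interval from the planned counts. All true. This limits the weight of the point, but it supplies neither a lower bound nor the missing table.

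**Conclusion.** The point holds as a modest improvement to the analysis and reporting. The planned interval is right for the primary endpoint and a poor match for the secondary one. At an assumed 5/7 to 7/7 per arm, the upper limit of 94.7–100% excludes almost nothing, while a two-sided interval would add a lower bound of 29–59%. At an assumed pooled 19/21, the limit is 98.3% against 70–98.8%. The size depends on the unknown true rate: near 47% the limit is still informative, and the loss grows as the rate rises. The mismatch in method does not depend on the exact rate.

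Separately, the routine low-grade tables rest on attribution, and no listed table presents solicited symptoms without it. How many events this would hide cannot be estimated from the documents and may be small.

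**What to change.** 1. In Section 9.2.1, limit the one-sided upper limit to the primary endpoint. In Section 9.3.4 or 9.3.8, specify a two-sided exact 95% interval for the Grade 1 or higher endpoint, per arm and for pooled vaccinees.
2. Reconcile Sections 8.1, 8.3.3, 8.3.4 and 10.1.9.1 so that every solicited local and systemic symptom from the log and the Day 2 and Day 7 assessments is entered, whatever its attribution. State how injection-site erythema and induration without functional interference are handled. Fix one symptom list: joint pain is on the log but not in Table 10.
3. Add one table to Section 9.3.8: maximum grade per participant for each solicited symptom, by arm and for pooled vaccinees against placebo, regardless of attribution. With 3 placebo recipients the comparison is descriptive only: 0/3 has a two-sided upper bound of 70.8%.

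The cost is a few sentences, one table and a little more data entry. No new visits, samples or participants are needed.

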9.2.1.1 Procedure for accounting for missing and unused data

Based on previous experience with similar trials, we anticipate that the amount of missing or invalid data will be small. All participants who are evaluable for adverse event assessment will be included in the safety analyses, regardless of whether they are replaced or missing for additional endpoints. Participants who do not start study treatment or are unable to provide the first or second leukapheresis will be replaced to achieve the planned evaluable sample size. Given the small size of this study, formal imputation methods will not be used. To assess whether key findings are sensitive to missing data, missing values can be replaced with worst possible outcomes as a sensitivity analysis (e.g., by replacing missing values in the M3 and M4 only arms with the best rank and replacing missing values in the M3+M4 arm with the worst rank, to assess if a finding regarding the M3+M4 arm is sensitive to missing data).

